8.4 Treatment Modification for Cardiopulmonary Events

Treatment modification for cardiopulmonary events is at the discretion of the treating physician. For the following events, it is suggested that the patient's treatment be held and their removal from protocol therapy should be considered:

- a. Decrease in cardiac ejection fraction of 10% from baseline.
- b. Development of NYHA Class III or IV heart failure (see Appendix [18.3](#)).
- c. Symptomatic cardiac arrhythmias other than isolated atrial fibrillation.
- d. Clinically significant cardiac ischemia.
- e. Pulmonary function testing is required and chest x-ray is strongly recommended in the event of Grade 3 or 4 dyspnea. The treating physician should consider holding treatment as outlined in Section [8.3](#); however dose modifications for dyspnea are at the discretion of the treating physician.

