 [name]
 [name]
 [name]

[contact]
 [contact] FAX

STATISTICAL CENTER
 [name]
 [name]
 [name]
 [contact]
 [contact] FAX

[name]
 [name]
 [name]
 [name]

[contact]
 [contact] FAX

swog.org

Study Chair: [name]
 [contact]
 E-mail: [contact]

IRB Review Requirements

- Full board review required. Reason:
 - Initial activation (should your institution choose to participate)
 - Increased risk to patient
 - Complete study redesign
 - Addition of tissue banking requirements
 - Study closure due to new risk information
- Expedited review allowed
- No review required

REVISION #5

The purpose of this revision is to update the protocol and Model Consent Form in accordance with the Amgen Safety Information, dated Tuesday 09 June 2015 (attached), which pertains to the following additional risk information from a recently-completed Phase III clinical trial and other safety information:

- i) Hypertension including hypertensive crisis
- ii) Pulmonary hypertension, and
- iii) Pulmonary Toxicities: Interstitial Lung Disease (including pneumonitis), Acute Respiratory Failure, and Acute Respiratory Distress Syndrome (ARDS).

1. The Version Date of the protocol and Model Consent Form have been updated.
2. Pages 3-4 Table of Contents: Content has been inserted into Section 3.1 on Page 13 and this has caused subsequent page numbers to shift.

3. Pages 11-13, Section 3.1: This section has been updated to be congruent with the information distributed in the 09 June 2015 Investigator letter and supporting documents:

- Section 3.1c.1: The following changes have been made to the Adverse Events with Possible Relationship to Carfilzomib table:
- The following risks were added:
 - Less Likely(4-≤20%):
 - ✓ Blood and Lymphatic System Disorders: Lymphopenia
 - ✓ Infections and Infestations: Bronchitis
 - ✓ Metabolism and Nutrition Disorders: Decreased appetite and Hypocalcemia
 - ✓ Skin and Subcutaneous Tissue Disorders: Diaphoresis
 - Rare but Serious (≤3%):
 - ✓ Blood and Lymphatic System Disorders: Thrombotic Thrombocytopenic Purpura/ Hemolytic Uremic Syndrome (TTP/HUS) and Thrombotic Microangiopathy
 - ✓ Cardiac Disorders: Hypertensive crisis
 - ✓ Gastrointestinal Disorders: Toothache
 - ✓ Infections and Infestations: Influenza
 - ✓ Nervous System Disorders: Posterior Reversible Encephalopathy Syndrome

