Based on substantial improvement in progression free survival observed in two Phase 3 trials in the relapsed multiple myeloma setting (Study PX-171-009 [carfilzomib in combination with lenalidomide and dexamethasone] and Study 2011-003 [carfilzomib in combination with dexamethasone]), the overall benefit: risk profile of carfilzomib remains favorable in subjects with relapsed/refractory multiple myeloma and other indications under study.

Actions Implemented by Amgen

- The Informed Consent Form (ICF) (in the Core Risks and Discomforts section) will be updated to inform subjects that events of hypertensive crises, pulmonary hypertension, and pulmonary toxicities have been observed in subjects receiving carfilzomib. Subjects will be advised to report signs and symptoms immediately to study personnel.
- Update the Investigator's Brochure (IB)
- Update the Company Core Safety Information (CCSI)

Actions for the Investigator

- Amgen requests that investigators communicate, by phone or in-person, the safety findings described above to study subjects receiving investigational product within 30 days of receipt of this notification.
- For subjects who are not currently receiving study drug, but are still participating in the study, investigators are requested to communicate the safety findings at the next regularly scheduled contact with the subject.
- Please ensure these communications to subjects are documented in the source medical records for the subject.

The revised informed consent form will be sent to you shortly. Please submit to your Ethics Committee/ Institutional Review Board per usual procedures.

- **For Hypertension including hypertensive crises**
- All patients should be routinely evaluated for hypertension and treated as needed. If the hypertension cannot be controlled, the carfilzomib dose should be reduced, per protocol. In case of hypertensive crisis, stop carfilzomib until resolved or returned to baseline and consider whether to restart carfilzomib based on a benefit/risk assessment.
- **For Pulmonary Toxicity**

- Evaluate and stop carfilzomib until resolved and consider whether to restart carfilzomib based on a benefit/risk assessment.
- **For Pulmonary Hypertension**
 - Stop carfilzomib until pulmonary hypertension has resolved or returned to baseline, and consider whether to restart carfilzomib based on a benefit/risk assessment.
- Please file a copy of this letter in your trial file.

[figure not shown]

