8.3 Dose Reductions for Toxicity

a. Carfilzomib

If a patient experiences any Grade 3 or 4 non-hematologic toxicity or Grade 4 hematologic toxicity in Cycle 1 that is considered to be related to study treatment, the second cycle of treatment will be given with carfilzomib at 20 mg/m^2 prior to escalation to the respective treatment dose for subsequent cycles. If a patient cannot undergo the dose escalation to the treatment dose despite being at 20 mg/m^2 for 2 cycles, they will be removed from protocol therapy.

Patients experiencing \geq Grade 3 non-hematologic or Grade 4 hematologic toxicity considered related to carfilzomib will have their treatment held until toxicity has resolved to Grade 2 or better. Supportive care should be administered per local institutional guidelines. When the toxicity has resolved, treatment will resume per the following guidelines:

- If the toxicity is resolved with supportive care prior to the next scheduled dose, carfilzomib treatment will be resumed at the same dose level.
- If the toxicity does not resolve until after the next scheduled dose, carfilzomib will be resumed at the next lower dose level as outlined in the dose reduction table below.

	Arm 1	Arms 2 and 3
Assigned Dose	27 mg/m^2	56 mg/m^2
Dose Level -1	20 mg/m^2	45 mg/m^2
Dose Level -2	15 mg/m^2	36 mg/m^2

- For patients whose drug toxicity does not resolve to Grade 1 or better (with the use of adequate supportive care) after 4 weeks of holding treatment, or who experience \geq Grade 3 non-hematologic or Grade 4 hematologic toxicity at Dose Level -2 will be removed from protocol treatment.

b. Dexamethasone

In general, dose reduction of dexamethasone is not allowed. However, in the case of Grade 3 or 4 gastrointestinal bleeding, dexamethasone may be discontinued, depending on clinical judgment of the treating physician. In case of dexamethasone discontinuation, premedication guidelines as mentioned below should be used and carfilzomib therapy will continue. For other Grade 3 or 4 toxicities with dexamethasone (including Grade 3 or 4 hyperglycemia despite adequate treatment with anti-hyperglycemic measures including insulin) rather than discontinuing the drug, dose may be reduced by up to 50% if side effects persist despite administration of supportive care per local institutional standards.

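### Section 8 does not carry the June 2015 letter's stop and restart rules for pulmonary toxicity, pulmonary hypertension and hypertensive crisis, and 8.3a and 8.4 treat such events differently without saying which prevails

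*Combined protocol and SAP*

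**What the plan says.** **The letter.** The 09 June 2015 letter was bound into the protocol with Revision #5, whose stated aim was to bring the protocol and consent form into line with it. For pulmonary toxicity it instructs: "Evaluate and stop carfilzomib until resolved and consider whether to restart carfilzomib based on a benefit/risk assessment". For pulmonary hypertension and hypertensive crisis the instruction is the same, except that return to baseline also ends the stop. No grade threshold is set.

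**Section 8.3a (general rule).** Patients with related non-hematologic toxicity of Grade 3 or higher "will have their treatment held until toxicity has resolved to Grade 2 or better". Then: "When the toxicity has resolved, treatment will resume per the following guidelines". The dose is unchanged if the event clears before the next scheduled dose, and one level lower if it does not. A later bullet removes patients after four weeks of holding and uses a different threshold: "For patients whose drug toxicity does not resolve to Grade 1 or better".

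**Section 8.4 (cardiopulmonary events).** It opens: "Treatment modification for cardiopulmonary events is at the discretion of the treating physician". For ejection-fraction decrease, NYHA Class III or IV heart failure, symptomatic arrhythmia and cardiac ischemia it only suggests that "treatment be held and their removal from protocol therapy should be considered". Item 8.4e, on Grade 3 or 4 dyspnea, points to 8.3 as something to consider: "however dose modifications for dyspnea are at the discretion of the treating physician".

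**Crossover.** Section 5.2c admits patients whose non-hematologic toxicity is Grade 2 or lower. Section 5.2d excludes those dose-reduced for toxicity in the last cycle before progression. Section 5.2f adds an ejection-fraction criterion. Under 7.4, Arm 3 starts at the full 56 mg/m2.

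**The concern.** Section 3.1 lists all three event types as carfilzomib risks, but the section that tells a site what to do about toxicity names none of them. A site that reads 8.3a as governing re-doses at Grade 2 with no benefit/risk step. A site that follows the letter through 8.4 waits for resolution (or baseline) and then decides whether to restart at all. Both can claim to follow the protocol. The same Grade 2 bar applies at crossover, where the next dose is about twice the Arm 1 dose.

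What is at stake is the safety of the few patients who have one of these events, through uneven handling between sites.

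**Working it through.** The plan gives no figure to reproduce here. The first check sets the texts side by side.

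| | Letter | 8.3a | 8.4 |
|---|---|---|---|
| Names the three events | Yes | No | No |
| Trigger | The event, any grade | Related, Grade 3 or higher (non-hematologic) | Physician judgement |
| Hold | Stop | Required | Suggested, for four listed cardiac events |
| End of hold | Resolved; or baseline for pulmonary hypertension and crisis | Grade 2 or better | Not stated |
| Restart | Considered on benefit/risk | Resumes by rule | Physician judgement |

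**Does any text rank 8.3a against 8.4?** Section 8.2b ranks concurrent toxicities by size of dose reduction, not one section against another. Item 8.4e settles it for dyspnea only. Calendar footnote 15 sends the reader to 8.5 for cardiopulmonary modification. The table of contents titles 8.5 as contacts, and its text was not in the copy reviewed. The conclusion is therefore limited to visible text.

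**Is 8.3a consistent in itself?** Resumption is at Grade 2, but removal applies to those not at Grade 1 after four weeks of holding. A patient who reaches Grade 2 has already resumed, so the mismatch has little practical effect. The Revision #5 change list says the resume threshold was moved from Grade 1 to Grade 2, so the removal bullet looks like leftover wording.

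**Who can reach Arm 3 with a Grade 2 event?**
- An event that clears to Grade 2 before the next scheduled dose resumes at the same dose. There is no reduction, so 5.2d does not exclude the patient.
- An event below Grade 3 needs no hold under 8.3a. Unless the physician reduces the dose, 5.2d does not apply.
- A related Grade 3 or higher event that outlasts the next scheduled dose resumes one level lower. If that happens in the last cycle, 5.2d excludes the patient.

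The gap is therefore events that led to no reduction in that cycle. The Arm 3 dose is 56/27 = 2.07 times the Arm 1 dose.

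**Scale.** The letter gives about 1% for pulmonary hypertension and under 1% for each of hypertensive crises and the pulmonary toxicities. The number of patients still on treatment when an amendment would take effect is not given, so assume n = 10, 20 or 40. Expected cases are n × p, and the chance of at least one is 1 − (1 − p)^n. With p = 0.01:

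| n (assumed) | Expected pulmonary hypertension cases | Chance of at least one |
|---|---|---|
| 10 | 0.1 | 1 − 0.99^10 = 10% |
| 20 | 0.2 | 1 − 0.99^20 = 18% |
| 40 | 0.4 | 1 − 0.99^40 = 33% |

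These rates cover a patient's whole exposure and are not grade-specific. The documents give no rate for these events at 56 mg/m2, so the table shows order of magnitude and is not an upper bound.

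**Time left.** Accrual stopped on 6 November 2015. Twelve cycles are 12 × 28 = 336 days, which takes the last entrants to about 7 October 2016 without delays. Revision #7, planned for about 15 February 2016, would have come up to 235 days (235/28 = 8.4 cycles) before that. Arm 3 allows up to 336 further days, to about October 2017.

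**The case against.** The strongest reply is that the instruction is already in force. The letter is addressed to investigators in active carfilzomib studies, is attached to the protocol, and is to be filed at the site. It asks for consent form, brochure and core safety updates, not for a dose-modification amendment. Section 8.4 is the more specific section, and its discretion fits the letter's restart step, which is itself a clinical judgement. A physician can comply with both at once.

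Most of this stands. A reader might infer that the protocol contradicts the letter, or that sites lack the instruction. The documents support neither; they show an omission and an ambiguity. What remains is that permission is not instruction. Section 3.0 has the protocol serve as the brochure for this IND, and nothing visible stops a site from applying 8.3a as written.

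A reader might also infer that any Arm 1 patient with a residual Grade 2 event may enter Arm 3. Section 5.2d rules that out for patients dose-reduced in the last cycle.

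It is fair, too, that whether each event can still be present at Grade 2 depends on CTCAE grading, which the documents do not reproduce. The gap between Grade 2 and resolved may therefore be wider for some of these events than for others.

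**Conclusion.** The point holds as a minor safety-drafting gap. Visible Section 8 does not carry the letter's stop and restart conditions, 8.3a and 8.4 lead to different handling, and only dyspnea is ranked. Section 5.2c permits full-dose crossover with residual Grade 2 toxicity unless 5.2d applies.

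The size is small: at the letter's rates, fewer than one expected case of pulmonary hypertension even among 40 assumed patients. Only cases handled under 8.3a or admitted through 5.2c would be treated differently after the change. Preventable events cannot be counted from the documents.

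Two stronger readings are not supported. A combined rate of 3% (1% for each category) exceeds what the letter reports for two of the three, which are each under 1%. And a reader might suspect bias in the dose comparison, but nothing in the documents shows an effect on it.

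The conclusion assumes that 8.5 contains contacts, as its title says, and that at least some of these events can persist at Grade 2.

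**What to change.** - In 8.4, add the three events with the letter's conditions: hold until resolved for pulmonary toxicity; hold until resolved or back to baseline for pulmonary hypertension and hypertensive crisis; restart only after a benefit/risk assessment.
- In 8.3a, state that 8.4 overrides the Grade 2 resume rule for these events, and bring the removal bullet (Grade 1) into line with the resume threshold (Grade 2).
- In 5.2c, apply the same condition before crossover.
- As a clerical point, calendar footnote 15 should probably cite 8.4.

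This is wording only, with no new procedures or data, and the planned Revision #7 could have carried it. The downside is slightly longer holds, a few removals under the four-week delay limit in 7.6f, and a few Arm 1 patients missing the 28-day crossover limit in 5.2b.

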8.6 Adverse Event Reporting

Toxicities (including suspected reactions) that meet the expedited reporting criteria as outlined in Section [16.0](#) of the protocol must be reported to the Operations Office, Study Chair and NCI via CTEP-AERS, and to the IRB per local IRB requirements.

9.0 STUDY CALENDAR

REQUIRED STUDIES ^{16, 19}	Pre-Study ²	Cycle 1				C2	C3	C4	C5	C6	C7	C8	C9	C10	C11	C12	Prog ¹⁴	FU ¹³	
		W1	W2	W3	W4	W5	W9	W13	W17	W21	W25	W29	W33	W37	W41	W45			
PHYSICAL																			
History and Physical Exam ¹	X	X				X	X	X	X	X	X	X	X	X	X	X	X	X	
Weight and Performance Status	X	X				X	X	X	X	X	X	X	X	X	X	X			
Toxicity Notation	X	X		X		X	X	X	X	X	X	X	X	X	X	X			
LABORATORY STUDIES																			
CBC, Diff, Platelets ³	X	X		X		X	X	X	X	X	X	X	X	X	X	X	X	X	
Bone Marrow Aspirate/Biopsy ⁴	X																	X	
Serum β2 Microglobulin	X																		
Complete Metabolic Panel ^{3,5}	X	X		X		X	X	X	X	X	X	X	X	X	X	X	X	X	
Serum Uric Acid	X		X		X														
CK, CK-MB, and BNP or pro-BNP ^{6,15}		C1 D1					After C3				After C6			After C9			After C12	X	
Troponin T and/or Troponin I		C1 D1					After C3				After C6			After C9			After C12		
C-reactive protein	X				X	X	X	X	X	X	X	X	X	X	X	X	X	X	
HIV/HepB/HepC Viral Load ⁷	X																		

Continued on next page

Click here to view [footnotes](#)

REQUIRED STUDIES ^{16, 19}	Pre-Study ²	Cycle 1				C2	C3	C4	C5	C6	C7	C8	C9	C10	C11	C12	Prog ¹⁷	FU ¹³
		W 1	W 2	W 3	W 4	W5	W9	W13	W17	W21	W25	W 29	W33	W37	W41	W45		
X-RAYS AND SCANS																		
Skeletal Survey ⁸	X																	X
EKG ^{9,15}	X					p Tx				p Tx		p Tx				p Tx		X
FDG-PET Scan ¹⁰	X															X ¹⁸		
ECHO ^{9,15}	X					p Tx				p Tx		p Tx				p Tx		X
RESPONSE ASSESSMENT																		
Serum Protein Electrophoresis ¹¹	X					X	X	X	X	X	X	X	X	X	X	X	X	X
Serum Quantitative Immunoglobulins ¹¹	X					X	X	X	X	X	X	X	X	X	X	X	X	X
24 hour Urine for: Total Protein ¹¹	X					X	X	X	X	X	X	X	X	X	X	X	X	X
24 hour Urine for: Protein Electrophoresis ¹¹	X					X	X	X	X	X	X	X	X	X	X	X	X	X
Serum and Urine Immunofixation Electrophoresis ¹¹	X					X	X	X	X	X	X	X	X	X	X	X	X	X
Serum Free Light Chains ¹¹	X					X	X	X	X	X	X	X	X	X	X	X	X	X
SPECIMEN SUBMISSION																		
Serum for Banking/Translational Medicine ¹²	X																	X
Biopsy and Aspirate for Banking/Translational Medicine ¹²	X																	X
Extramedullary Aspirate/Core ¹²	X																	X
TREATMENT ¹⁴																		
Dexamethasone	X	X	X			X	X	X	X	X	X	X	X	X	X	X	X	
Carfilzomib	X	X	X			X	X	X	X	X	X	X	X	X	X	X	X	

Continued on next page

Click here to view [footnotes](#)

NOTE: Forms are found on the protocol abstract page on the SWOG website (www.swog.org). Forms submission guidelines are found in Section [14.0](#).

Footnotes for Study Calendar:

- 1 To be performed on Day 1 (\pm 3 days) of each cycle. H&P should include CTCAE Grade assessment of neuropathy.
- 2 Labs and physical assessment on Cycle 1 Day 1 may be omitted if pre-study labs were performed within 4 days of Cycle 1 Day 1. Results of Day 1 labs are not required prior to starting treatment for each cycle. If lab results do show existence of adverse events, the treating physician should refer to [Section 8.0](#), and otherwise continue treatment at their discretion.
- 3 Pre-study (within 14 days prior to registration), during Weeks 1 and 3, then every cycle or more often if clinically indicated.
- 4 Pre-study (within 28 days prior to registration) then as clinically indicated. Aspirate/biopsy is required at progression with patient consent.
- 5 Including magnesium, phosphate, sodium, potassium, chloride, bicarbonate, glucose, BUN, creatinine, bilirubin, SGOT/SGPT, calcium, albumin, LDH.
- 6 To be performed at baseline (Day 1 of Cycle 1), after Cycles 3, 6, 9, and 12 and at completion of treatment for any reason (unless performed within previous 28 days). For patients who cross over, to be performed every 3 cycles based on previous date of measurement.
- 7 Tests required for patients known to be positive for HIV, HepB or HepC to determine viral load; optional for all others. Pre-study to be done within 28 days prior to registration, if required.
- 8 Pre-study to be done within 28 days of registration, and at the time of documented disease progression or as clinically indicated.
- 9 Pre-study (within 28 days prior to registration), then after completion of treatment on Cycles 3, 6, 9 and 12, and at completion of treatment for any reason (unless EKG or ECHO has been performed within previous 28 days). For patients who cross over, to be performed every 3 cycles based on date of previous measurement. Crossover patients do not need to repeat Cycle 1 Day 1 tests, as long as patient is starting Arm 3 treatment within 28 days of prior testing (at time of progression) and the previous test results did not show a significant change from baseline. See Section [15.3](#) for ECHO imaging information, and Appendix [18.2](#) for AG Mednet image submission instructions.
- 10 See Section [15.1](#) for PET imaging information, and Appendix [18.2](#) for AG Mednet image submission instructions.
- 11 Pre-study (within 14 days prior to registration), then on Day 1 (\pm 3 days) of Cycles 2-12, then monthly until disease progression, at disease progression and at all follow up visits.
- 12 See Section [15.2](#).
- 13 Every 3 months after removal from protocol therapy for up to 3 years after initial registration, or more often if clinically indicated. For study purposes, response assessments (SPEP, immunoglobulins, 24 hour urine, serum/urine IFE, and CRP) are no longer required after progression or removal from trial due to toxicity.
- 14 See Section [7.0](#).
- 15 See Section [8.5](#) for treatment modification for cardiopulmonary events.
- 16 Unless otherwise noted, all required studies are to be performed on Day 1 of the treatment cycle.
- 17 At the time of progression, patients on Arm 1 may cross-over to Arm 3, providing they meet the additional criteria outlined in Section [5.2](#).
- 18 For patients with extramedullary progression (EMP), a follow-up PET scan at the end of treatment or at the time of VGPR, whichever occurs earlier, is required. See Sections [15.1](#) and Appendix [18.2](#) for requirements.
- 19 For patients that crossover to Arm 3, return to Cycle 1, Day 1, and follow the same study calendar. Assessments completed at time of progression on Arm 1, do not need to be repeated on Arm 3 (crossover) C1, D1, provided that ANC, platelets, SGOT, SGPT, serum creatinine, SPEP, and lambda light chain assessments are accomplished within 14 days prior to registration to Arm 3. All other assessments may have been accomplished anytime within 28 days prior to registration to Arm 3 (i.e. at time of progression on Arm 1). Note: Per eligibility criterion 5.2b, at least 14 days and no more than 28 days must have elapsed between the last day of treatment on Arm 1 and registration to Arm 3.

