7.3 Registration Step 1 – Initial Registration (Arms 1 and 2)

a. Carfilzomib Dosing

For both treatment arms of the initial registration (Arms 1 and 2), carfilzomib will be administered at a dose of 20 mg/m^2 for Cycle 1. If tolerated in Cycle 1, the dose will be escalated to 27 mg/m^2 (Arm 1) or 56 mg/m^2 (Arm 2) beginning in Cycle 2 and continued in subsequent cycles. Note: Dose rounding is acceptable at the discretion of the treating physician; this must be documented on the **S1304** Treatment Form.

The carfilzomib dose will be calculated using the patient's actual body surface area at baseline. Patients with a body surface area greater than 2.2 m^2 should receive a dose based upon a body surface area of 2.2 m^2 . Dose adjustments do not need to be made for weight changes of less than or equal to 20%.

If a patient experiences any Grade 3 or 4 non-hematologic toxicity or Grade 4 hematologic toxicity in Cycle 1 that is considered to be related to study treatment, the second cycle of treatment will be given with carfilzomib at 20 mg/m^2 prior to escalation to the respective treatment dose for subsequent cycles. If a patient cannot undergo the dose escalation to the treatment dose despite being at 20 mg/m^2 for 2 cycles, they will be removed from protocol therapy.

b. Arm 1 – Dexamethasone + Low Dose Carfilzomib

Agent	Dose	Route	Day	Schedule*
Dexamethasone ^b	20 mg	IV	1, 2, 8, 9, 15, 16	up to 12 cycles
Carfilzomib ^a	20 mg/m^2	IV over 2-10 mins	1, 2, 8, 9, 15, 16	Cycle 1
Carfilzomib	27 mg/m^2	IV over 2-10 mins	1, 2, 8, 9, 15, 16	Cycles 2-12

* Note: 1 cycle = 28 days

^a See Section [7.3a](#) for Cycle 1 carfilzomib dosing and for dose capping based on BSA.

^b On all treatment days, dexamethasone will be administered 30 minutes prior to the carfilzomib infusion.

c. Arm 2 – Dexamethasone + High Dose Carfilzomib

Agent	Dose	Route	Day	Schedule*
Dexamethasone ^b	20 mg	IV	1, 2, 8, 9, 15, 16	up to 12 cycles
Carfilzomib ^a	20 mg/m^2	IV over 2-10 mins	1, 2, 8, 9, 15, 16	Cycle 1
Carfilzomib	56 mg/m^2	IV over 30 mins	1, 2, 8, 9, 15, 16	Cycles 2-12

* Note: 1 cycle = 28 days

^a See Section [7.3a](#) for Cycle 1 carfilzomib dosing and for dose capping based on BSA.

^b On all treatment days, dexamethasone will be administered 30 minutes prior to the carfilzomib infusion.

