7.6 Criteria for Removal from Protocol Treatment

- a. Progression of disease or symptomatic deterioration (as defined in Section [10.5](#)) **for patients being treated with higher dose (56 mg/m²) carfilzomib.**
- b. Completion of 12 cycles of low dose carfilzomib on Arm 1 or 12 cycles of high dose carfilzomib.
- c. Unacceptable toxicity.
- d. Patient is unable to dose-escalate to assigned dose (27 mg/m² or 56 mg/m²) after 2 cycles of therapy.
- e. Permanent discontinuation of carfilzomib.
- f. Treatment delay for any reason > 4 weeks.
- g. The patient may withdraw from the study at any time for any reason.

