10.5 Progression-Free Survival

From date of registration to date of first documentation of progression or symptomatic deterioration (as defined below), after having received the full-assigned Arm-specific dose of carfilzomib (27 mg/m² or 56 mg/m²), or death due to any cause. Patients last known to be alive and progression-free are censored at date of last contact.

Symptomatic Deterioration: The global deterioration of health status requiring discontinuation of treatment without objective evidence of progression.

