14.4 Data Submission Overview and Timepoints

- a. WITHIN 7 DAYS AFTER INITIAL REGISTRATION (STEP 1):

Submit the following:

S1304 Onstudy Form

FDG-PET and ECHO Images (see Appendix [18.2](#)). Retrospective ECHO image submission will also be requested for all patients.

PET Report

Specimens for TM and Banking (see Section [15.2](#))

- b. WITHIN 14 DAYS FOLLOWING EACH TREATMENT CYCLE:

Submit the following:

S1304 Treatment Form

Adverse Event Form

Follow-up Tumor Assessment Form for Multiple Myeloma

- c. AFTER COMPLETION OF CYCLES 3, 6, 9 AND 12 (including crossover to Arm 3):

Submit the following:

S1304 Cardiac Assessment Form

ECHO Images (see [Appendix 18.2](#)) (For crossover patients, ECHOs must be submitted every 3 cycles from the date of previous measurement.) Retrospective ECHO image submission will also be requested for all patients.

- d. WITHIN 7 DAYS OF ACHIEVING VGPR OR BETTER:

Submit the following:

FDG-PET and ECHO Images (see Appendix [18.2](#)). Retrospective ECHO image submission will also be requested for all patients.

PET Report

e. WITHIN 14 DAYS OF FIRST PROGRESSION/RELAPSE (ARMS 1 AND 2):

Submit the following:

Follow-up Tumor Assessment Form for Multiple Myeloma (if the patient was still on protocol treatment) or Follow-Up Form (if the patient was off protocol treatment) documenting date, site and method for determining progression/relapse.

Specimens for TM and Banking (see Section [15.2](#))

f. WITHIN 14 DAYS OF CROSSOVER REGISTRATION (STEP 2):

Submit the **S1304** Step 2 Eligibility Form

g. WITHIN 14 DAYS OF SECOND PROGRESSION/RELAPSE (ARM 3):

Submit the following:

Follow-up Tumor Assessment Form for Multiple Myeloma (if the patient was still on protocol treatment) or Follow-Up Form (if the patient was off protocol treatment) documenting date, site and method for determining progression/relapse.

Specimens for TM and Banking

h. WITHIN 14 DAYS OF DISCONTINUATION OF TREATMENT:

Submit the following:

Off Treatment Notice

S1304 Treatment Form

Adverse Event Form

(for patients with extramedullary disease) FDG-PET Image, unless submitted for VGPR (see Appendix [18.2](#))

ECHO Images (see [Appendix 18.2](#)). Retrospective ECHO image submission will also be requested for all patients.

S1304 Cardiac Assessment Form (if ECHO is performed)

i. EVERY 3 MONTHS AFTER OFF TREATMENT FOR UP TO 3 YEARS FROM INITIAL REGISTRATION:

Submit the Follow-up Form

j. WITHIN 4 WEEKS OF KNOWLEDGE OF DEATH:

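### M-protein testing may stop after removal for toxicity while PFS is censored at last contact, so untested time can count as progression-free; PFS is biased if toxicity removals differ by arm

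*Combined protocol and SAP*

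**What the plan says.** - **Testing.** Section 9.0, footnote 13, sets follow-up every 3 months after a patient leaves protocol therapy. It then says that SPEP, immunoglobulins, 24-hour urine, serum/urine immunofixation and CRP "are no longer required after progression or removal from trial due to toxicity". The Revision #5 summary lists the toxicity waiver as an intended clarification.
- **A competing footnote.** Footnote 11 covers the same M-protein tests and asks for them "then monthly until disease progression, at disease progression and at all follow up visits", with no exception for toxicity.
- **Censoring.** Section 10.5: "Patients last known to be alive and progression-free are censored at date of last contact".
- **Contact.** Section 7.8 follows everyone to death or 3 years. Section 14.4i requires a form "EVERY 3 MONTHS AFTER OFF TREATMENT FOR UP TO 3 YEARS FROM INITIAL REGISTRATION".
- **Reporting off treatment.** At first progression, Section 14.4e takes the tumor assessment form "or Follow-Up Form (if the patient was off protocol treatment) documenting date, site and method for determining progression/relapse".
- **Analysis.** Section 11.3 compares PFS by intent to treat with a stratified log-rank test, at 100 progressions or at the latest 2 years after the last patient. Section 11.2 sets one-sided alpha at 0.1.

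**The concern.** The serum and urine progression criteria in Section 10.1b need the waived tests. Free light chains are not on the waiver list. However, Section 10.1b applies the light-chain criterion only to patients whose serum and urine M protein were both below the measurable limits at baseline, so it does not fill the gap for the others.

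A patient removed for toxicity can thus progress biochemically without a test, stay in contact every 3 months, and be censored as progression-free at the last contact. The quality of ascertainment then depends on an outcome that arises after randomisation and may depend on dose. The log-rank comparison would credit the arm with more toxicity removals with event-free time that nobody verified. Section 11.7 does not guard against this: it compares toxicity rather than removal, at 20 patients per arm, and is powered (at least 83%) for a 40-point difference.

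**Working it through.** **1. The plan's own figures.** Inputs from Sections 11.2 and 11.3: one-sided alpha 0.10, power 0.90, hazard ratio 1.67 (medians 9 and 15 months), 63 per arm, 21 months' accrual, 18 months' follow-up.

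Events (Schoenfeld) = 4(1.2816 + 1.2816)² / (ln 1.67)² = 26.28 / 0.263 = 100.

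Expected events per arm = 63 × [1 − (e^(−18λ) − e^(−39λ)) / (21λ)], with λ = ln 2 / median. This gives 55.2 (median 9) + 45.4 (median 15) = 100.6. The design figures reproduce, so the problem lies in ascertainment and censoring, not in the sample size.

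**2. Assumptions not in the documents.** A share of each arm is destined for toxicity removal, spread evenly over months 1 to 8. A share of the progressions after removal is still captured. A missed progression becomes an event at death, with a median of 12 or 24 months from progression to death.

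Fraction of destined patients removed before progression, at median 9 (λ = 0.0770) = (e^(−λ) − e^(−8λ)) / (7λ) = (0.926 − 0.540) / 0.539 = 0.716. So 10%, 20% and 30% destined means about 7%, 14% and 21% removed, or 4.5, 9.0 and 13.5 of 63 patients.

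**3. Simulation.** Exponential PFS, uniform accrual, cut at the 100th event or month 45 (21 + 24), contact to 36 months, last-contact censoring, unstratified log-rank. Without removals, type I error is 0.10 and power 0.90.

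One-sided type I error with no true effect (ranges cover 12 and 24 months to death):

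| Destined for removal, Arm 1 vs Arm 2 | 90% captured | Half captured | Deaths only |
|---|---|---|---|
| 10% vs 20% | 0.11 to 0.12 | 0.13 to 0.16 | 0.17 to 0.22 |
| 10% vs 30% | 0.12 to 0.13 | 0.18 to 0.22 | 0.29 to 0.38 |

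- 10% vs 15%: about 0.09 to 0.12 with 90% or half captured.
- Equal removal: type I error 0.10. Power is about 0.86 to 0.88 at 10% per arm and 0.82 to 0.88 at 20% per arm, from deaths only up to half captured.
- Mirror case (20% in Arm 1, 10% in Arm 2) with at least half captured: type I error 0.07 to 0.10, power 0.83 to 0.88.

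**4. Dependence on the model.** A variant with removal spread over 12 cycles and deaths ignored gives 0.17 and 0.27 at half capture for the two rows above. It overstates the problem, because death is a PFS event, but it shows that the sizes are illustrations.

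**5. Censoring at the last assessment.** With later events and later event-free time treated alike, type I error returns to about 0.10 to 0.11. If progressions found clinically after removal are counted but event-free patients are censored at removal, it falls to 0.06 to 0.09, a bias the other way.

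**The case against.** **Detection remains.** Follow-up keeps history and physical, CBC and metabolic panel. Free light chains, bone-lesion, plasmacytoma and marrow criteria, hypercalcemia, off-treatment progression reports and death all remain. A test that is not required is also not forbidden. This stands. A reader might infer that only deaths can be seen after toxicity removal; the documents do not say so, and the deaths-only column is an extreme.

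**A milder reading exists.** Section 10.5 speaks of patients *known* to be progression-free, and an untested patient arguably is not. Footnote 13 also uses two terms, removal from protocol therapy and removal from trial. If the second ends contact, little untested time accrues. Both readings are possible, but the text secures neither: the stated censoring date is last contact, and removal from trial is not defined.

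**Nothing shows an imbalance.** A reader might infer that PFS is biased towards the higher dose. The documents do not support that. Section 2.0 expects the higher dose without significant additional toxicity. Its only related figures are cardiac: 23 of 526 (4%) stopped for a cardiac event in earlier studies, and Grade 3 or higher heart failure was 6% both there and in 65 patients at 20/56 mg/m². These do not bound all-cause removal, but they show no gradient between doses. The direction and size of any bias are conditional.

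**Conclusion.** The point holds in conditional form. Following the plan as written, untested time after toxicity removal can enter the primary analysis as progression-free time. The direction follows from the rule: the arm with more toxicity removals looks better. The size does not follow from the documents. It is negligible to small at 10% vs 15% or with 90% capture. It is material (0.13 to 0.22 against 0.10) at 10% vs 20% or 30% with half captured. With equal removal the cost is power, not validity. The upper value of 0.38 needs both a 20-point gap and no detection short of death, and should not be read as an estimate.

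This should be fixed, with medium confidence: the gap in the text is clear, its effect is assumption-dependent, and most of the remedy is wording and one analysis.

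**What to change.** 1. **Censoring.** In Section 10.5, censor patients without an event at the last adequate disease assessment, and state how a progression or death after an assessment gap is handled, treating events and event-free time after the gap alike. As a minimum, prespecify this as a sensitivity analysis beside the last-contact analysis. In either case report toxicity removals and assessment completeness by arm. *Cost:* it assumes that removal is unrelated to prognosis, and it loses events. At 10% vs 30% with nobody assessed after removal, there are about 86 events and power 0.85 at month 39, or 91 events and 0.87 at month 45, against 100 and 0.90. Section 14.4 does not show that dates of negative off-treatment assessments are collected, so sites may have to supply them. Accrual is permanently closed, and assessments already missed cannot be recovered.
2. **Calendar.** Reconcile footnotes 11 and 13 on whether and how often assessments continue after toxicity removal, and define removal from trial. *Cost:* wording; any added tests burden patients who left because of toxicity.
3. **Separate point.** Section 10.5 counts progression only "after having received the full-assigned Arm-specific dose of carfilzomib". Patients removed under Section 7.3a ("If a patient cannot undergo the dose escalation to the treatment dose") or 7.6d ("Patient is unable to dose-escalate to assigned dose") can, as written, have only death as a PFS event, whatever testing is done. Reconcile this clause with the intent-to-treat analysis in Section 11.3.
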